Title Page

Study Protocol with Statistical Analysis Plan

Official Title:	Pilot study of creatine monohydrate as an augmenting agent for	
	electroconvulsive therapy in persons with major depressive disorder	
NCT Number:	NCT04504253	
Document Date	01MAR2020	
Principal	[name], PhD; [name], PhD	
Investigators		
Co-Investigators	[name]; [name]; [name]; [name]	
	[name]; [name], PhD, MBA	

I. Introduction

We propose to determine if augmentation of electroconvulsive therapy (ECT) utilized for the treatment of major depressive disorder (MDD) with daily oral creatine will lead to an accelerated response to treatment, an overall increase in response rate, and will protect against cognitive adverse effects associated with ECT. We propose to conduct a two-arm, parallel, randomized, double-blinded, placebo-controlled trial, with a treatment group receiving 20 g oral loading dose of creatine for 1 week starting the day before initiating ECT, followed by 5 g oral creatine daily for roughly five weeks, including the approximately three-week ECT treatment course and a two-week follow-up period. Response to treatment will be assessed using the Quick Inventory of Depressive Symptomatology (QIDS) at each treatment and the 17-item Hamilton Depression Rating Scale (HAM-D17) at the end of each week.

II. Background and Significance

A. Prevalence and Impact of Depression

MDD has a lifetime prevalence of over 16%[1] and is associated with significant personal and social costs, including lost work productivity [2], disability [3, 4], diminished quality of life, increased mortality [5], increased rates of suicide attempts [6] and completed suicides [7, 8]. The financial impact of depression in the United States is significant, with an estimated economic burden of individuals with MDD of approximately \$210.5 billion dollars annually, including direct costs, suicide-related costs, and workplace costs [9]. Although MDD is often regarded as a single disorder, it may encompass a variety of different etiologies with overlapping symptoms and signs [10, 11]. An additional complication of MDD is the high risk of disease recurrence; the presence of two or more chronic medical conditions, female gender, never having been married, activity limitation, and less contact with family are all significant predictors of MDD persistence [12].

MDD can be challenging to treat clinically, especially due to its propensity to be treatmentresistant. Treatment-resistant Depression (TRD) is currently defined as failure to achieve remission after two or more adequate pharmacologic trials [14, 15]. Current literature suggests that the majority of individuals with MDD do not reach and subsequently maintain a fully remitted state [16]. Furthermore, results from the STAR-D trial indicate that the overall likelihood of failure to achieve remission is increased with increasing number of failed medication trials [17]. At this time, the adjunctive use of atypical antipsychotics has been well-investigated, but less is known about alternative adjunctive agents [16].

Current clinical guidelines for the treatment of depression establish basic principles for establishing a treatment plan, preparing for potential need for long-term treatment, and assessment of remission. For moderate major depression, first line treatment includes antidepressant monotherapy and psychotherapy. For severe major depression, antidepressant therapy can be augmented with an antipsychotic or ECT [18]. Due to the overall disease burden of unmanaged MDD, the prevalence of treatment resistant depression, high rates of primary treatment failure, the additional study of alterative adjunctive therapy is both appropriate and potentially impactful.

B. Efficacy of ECT in Treatment of MDD

ECT is considered to be a first line treatment for depression with psychotic features, but it is also often used to treat patients with treatment-resistant depression (TRD) [19]. According to a 2015 metanalysis, approximately one third of patients with MDD do not respond to ECT, with failed medication trials and longer depressive episodes being the strongest predictors of poor response [20]. For treatment-resistant depression, the overall response rate is approximately 58%, compared to a 70% response rate in patients without TRD [20]. When assessing the overall

efficacy of ECT, both remission and response are used, although remission is more frequently used in clinical practice. In general, response has been defined as a 50% decrease in baseline depression screening scores, while remission is defined as a score <7 on the HAM-D17, or <10 with the 24-item HAM-D [19].

Assessments of remission in MDD after ECT treatment suggest that chronic depression, medication resistance, longer episode duration, and younger age are all statistically significant predictors of non-remission [21]. Remission rates in ECT tend to be robust; data from the CORE trial suggested an overall remission rate of 87%, which further delineates into 95% remission rate with the presence of psychotic features and 83% without [22]. Again, however, rates of response and remission with ECT are lower for patients with treatment-resistant depression, who may make up the majority of patients receiving ECT in clinical samples.

Although ECT is an effective treatment for MDD, up to one third of patients experience significant memory loss and other adverse cognitive effects after receiving ECT [23]. Strategies to limit ECT's effects on memory, such as altering electrode placement (e.g., from bitemporal to bifrontal), ensuring days off between treatments, and modulating pulse width, amplitude, and frequency, may all have some benefit[24]. Still, cognitive complaints remain one of the most significant side-effects of ECT, and concerns about these effects represent a major reason that patients who could benefit from ECT choose not to pursue it. [23]. Nootropic agents, thyroid hormone, and donepezil have all been studied to mitigate the cognitive side effects, but no consistent benefit has been shown and no current adjunctive medication is recommended [24].

C. ECT Augmentation

In order to maximize the efficacy of ECT in the treatment of MDD, several studies have analyzed the benefit of augmentation with a variety of antidepressants, anesthetic agents, and nutritional supplements. The most thoroughly studied has been adjunctive ketamine administration with ECT, although findings have been inconsistent. A metanalysis of RCTs investigating adjunctive ketamine and ECT in 2019 did not find that ketamine improves the efficacy of ECT when compared to other anesthetic agents, although it was suggested that ketamine could lead to improvement of depressive symptoms in the acute phases of ECT when used in combination [25]. There was no improvement in depressive symptoms with ketamine augmentation by the end of the ECT series [25]. The effect of ketamine on the neurocognitive side effects associated with ECT remains unclear, but no clear benefit has been shown [25]. In addition, the long-term efficacy and safety of ketamine use in ECT is unknown, particularly in the setting of maintenance treatment.

Many secondary agents have been studied in conjunction with ECT therapy, including caffeine sodium benzoate (CSB), hyperventilation, and methylxanthines [26]. However, these agents have primarily been studied for their potential to lower seizure threshold or increase overall seizure duration during ECT, without clear effects on overall ECT efficacy or symptom improvement apart from effects on seizure characteristics [26]. Less is understood about the effects of nutritional supplementation, such as folate, thyroid hormone, tryptophan, or S-adenosylmethionine (SAM-e). A case study from 2015 demonstrated improvement in response to ECT after folate supplementation [27].

There is some research that has demonstrated associations between response/remission in ECT and serum levels of various vitamins and essential nutrients. A 1994 study examining the association between serum 5-methyltetrahydrofolate (5-MeTHF) levels and ECT response did not demonstrate any significant association between ECT response and serum 5-MeTHF levels, although low serum 5-MeTHF levels were positively correlated with depression symptom severity [28]. A pilot study has further analyzed serum levels of vitamin B12, folate, S100B, homocysteine, and procalcitonin in patients undergoing ECT, and found that decreased vitamin B12 and folate levels in conjunction with elevated homocysteine and S100B levels lead to increased sensitivity to ECT, as evidenced by increased remission rates [29]. Thyroid hormone has been studied in

the setting of ECT therapy, both as an adjunctive treatment for depressive symptoms and as an agent to reduce neurocognitive deficits associated with ECT and has been demonstrated to reduce ECT associated amnesia and promote a decrease in depressive symptoms [30]. Still, thyroid hormone has not been widely used in clinical practice, possibly because of concerns about adverse effects.

D. Creatine and Depression

There is a growing body of literature surrounding the use of standardized, pharmaceutical-grade nutrients (nutraceuticals) as augmentation therapy in the setting of treatment resistant depression. A 2016 metanalysis concluded that adjunctive use of SAM-e, I-methylfolate, omega-3, and vitamin D with antidepressant therapy leads to a reduction in depressive symptoms, while isolated studies showed a similar effect with the use of creatine, folinic acid, and an amino acid combination [31].

Creatine is a naturally-occurring organic acid that is known to play a role in brain energy homeostasis and is hypothesized to be involved in the pathophysiology of depression via altered energy metabolism [31]. Oral creatine supplementation has been shown to increase cerebral phosphocreatine levels, which is hypothesized to shift cerebral creatine kinase activity, leading to increased ATP production [32-34]. Early literature suggests that creatine may have an antidepressant effect when used as adjunctive therapy in MDD, due to its role in altering brain bioenergetics [35]. Creatine has been shown to lead to an earlier treatment response in patients treated with escitalopram, with positive response to therapy as early as 2 weeks after beginning treatment [34]. To date, no studies have investigated the use of creatine as an adjunctive therapy to ECT.

Inadequate tissue bioenergetic functioning is thought to be related to disease pathology that affects predominately organs that are comparatively highly metabolically active, like the brain, liver, heart, and skeletal muscle [36]. Because creatine supplementation has the potential to increase bioenergetic stores, it may produce an antidepressant response by enabling synaptogenesis, increasing connectivity between frontal cortical regions and the amygdala, or enhancing frontal cortical functioning. ECT is thought to produce an antidepressant effect largely by promoting synaptogenesis in frontal cortical regions via alterations in the activity of NMDA and AMPA receptors, leading to upregulations in BDNF. Accordingly, creatine has the potential to augment the efficacy of ECT by increasing bioenergetic stores available for synaptogenesis. There is also some evidence to suggest that creatine has activity at NMDA receptors, functioning as a neuromodulator that is released in response to electrical stimulation [37]. Its activity at NMDA receptors is potentially another explanation for its antidepressant effect.

In a mouse model study of hyperhomocystinemia, a condition that leads to impaired creatine kinase activity, creatine supplementation was shown to have neuroprotective effects, with suggestion of memory improvement [38]. Other mouse model studies have shown that creatine can generate improvement of spatial memory, when compared to a traditional diet, as well as improve learning and mitochondrial function[39, 40]. Several human studies have also demonstrated that creatine supplementation is associated with multiple cognitive improvements, including effects on attention, mood, working and long-term memory, and mental fatigue [41-45]. These data suggest that creatine is a potential approach for addressing the cognitive side effects associated with ECT therapy.

E. Creatine Safety and Toxicity

Retrospective and prospective studies in humans have found no evidence for long-term or shortterm significant side effects from creatine supplementation taken at recommended doses [46-49]. Most controlled studies of creatine report an absence of side effects or report no differences in the incidence of side effects between creatine and placebo [50]. Mihic and colleagues (2000) have demonstrated that creatine loading increases fat-free mass, but does not affect blood pressure or plasma creatinine in adult men and women. Reports in the popular media of links between creatine use and muscle strains, muscle cramps, heat intolerance, and other side effects are not supported by the medical literature [50]. Studies conducted in athletes and military personnel indicate a substantial safety level of both short- and long-term creatine supplementation in healthy adults [51-56]. Concerns about high-dose creatine's association with renal toxicity are based exclusively on two published case reports; in one of the cases the patient had a documented pre-existing kidney condition [57, 58]. Literature reviews and expert consensus panels have concluded there is no evidence supporting an association between creatine and renal disease [59-62].

Concern has been raised regarding creatine's potential for adverse effects on the kidneys and renal system, in part because creatine supplementation can increase urinary creatine and creatinine excretion [63]. In response to the concerns regarding creatine and renal toxicity, Poortman's conducted studies of the effect of creatine supplementation on renal function, showing that short-term supplementation does not alter glomerular filtration rate [47], and that chronic supplementation of up to five years' duration did not impair renal function in healthy athletes [49].

[64] conducted a retrospective study of participants who had been taking oral creatine from 0.8 to 4 years, at an average dose of 9.7 grams per day. Data was collected on 65 health-related variables. These included a complete blood count, 27 serum chemistries, and anthropometric data including vital signs and % body fat. On all 65 variables, group means fell within the normal clinical range. The authors concluded that that long-term creatine supplementation does not result in adverse health effects.

Evidence to date suggests that even aged, debilitated, medically fragile patients are able to tolerate creatine supplementation. Bender and colleagues studied elderly patients with Parkinson's Disease who had received either placebo or four grams/day of creatine for two years. They found no differences between the creatine and placebo groups in laboratory markers of renal dysfunction [65]. Interestingly, the participants who received creatine performed better on the depression subscale of the Unified Parkinson Disease Rating Scale [66].

No strong evidence exists linking creatine supplementation and gastrointestinal discomfort. These reports remain anecdotal, as there are no documented reports of creatine over placebo resulting in stomach concerns.

III. Specific Aims

Aim 1: To evaluate the effect of creatine supplementation on response to ECT over the course of 6 weeks among persons with MDD. We hypothesize: 1) that creatine will increase response rates to ECT compared to placebo, as determined by a > 50% reduction in HAM-D17 scores earlier in treatment course as compared to placebo; 2) that creatine supplementation will increase remission rates (HAM-D17 < 7) in persons receiving ECT for MDD, compared to placebo; and 3) that creatine supplementation will reduce the time to response and remission among ECT recipients compared to placebo.

Aim 2: To evaluate the effect of 6 weeks of creatine supplementation on ³¹P-MRS neuroimaging data among persons with MDD. We hypothesize that creatine supplementation of persons with MDD receiving ECT will promote increases in frontal cortical concentrations of phosphocreatine (and phosphocreatine to total phosphorus ratios) relative to baseline, while placebo supplementation will have no impact on phosphocreatine levels.

Aim 3: To determine if creatine supplementation throughout an ECT course leads to decreased cognitive adverse effects of ECT as measured by changes in the Montreal Cognitive Assessment (MoCA) score, compared to placebo. We hypothesize that creatine augmentation during ECT therapy will be protective against cognitive adverse effects, as measured by changes in subjects' MoCA scores between baseline and 8 weeks, when compared to placebo.

IV. Methods

A. Eligibility Criteria

Participants with a diagnosis of Major Depressive Disorder with moderate to severe symptoms will be randomly assigned in a 1:1 ratio to either ECT with creatine augmentation or ECT with placebo augmentation or 6 weeks. Individuals must meet criteria for major depressive episode for a duration of at least 2 months in order to participate. Participants must be greater than 18 years of age and considered to be a good candidate for ECT based on clinical assessment. Individuals who are pregnant or breast-feeding or who possess any other contraindication to ECT will not be invited to participate. Participants can receive ECT treatments in either inpatient or outpatient setting at the University Neuropsychiatric Institute.

Individuals who meet diagnostic criteria for other psychiatric conditions apart from major depressive disorder (including Bipolar I, Bipolar II, or personality disorders) will not be invited to participate. Individuals with substance use disorders will be excluded because substance use disorders typically confound the diagnosis of depression and can contribute to treatment resistance. Individuals will not be considered for study participation if they have *renal disease* because to date it cannot definitively be stated if short and long-term creatine usage is or is not harmful to the kidneys. Appropriate renal function will be determined based on normal creatinine clearance, determined by routine laboratory work (basic metabolic panel).

Participants who are already undergoing electroconvulsive therapy (ECT) or transcranial magnetic stimulation (TMS) for the treatment of depression, or who have completed a course of ECT within a month of the baseline visit, will not be invited to participate given the possibility of confounding treatment effects as well as increased seizure risk. Individuals currently undergoing psychotherapy remain eligible to participate.

Participants who have implanted ferromagnetic hardware, implanted electronic devices, or retained ferromagnetic materials from surgery or injuries will not be invited to participate as these represent contraindications to MRI. Likewise, individuals who are unable to tolerate confinement in the MRI scanner will not be invited to participate.

Individuals who lack capacity to consent to treatment or to participate in the study will be excluded. Patients who are hospitalized involuntarily will also be excluded. Individuals demonstrating active psychosis or any other clinical characteristic making them inappropriate candidates for treatment will be excluded. Patients with pre-existing neurologic condition, any major neurocognitive disorder, or known traumatic brain injury will not be invited to participate.

B. Study Withdrawal Criteria

A participant will be withdrawn from the study he/she experiences intolerable or clinically significant side effects to creatine, hospitalization for suicidal ideation or suicide attempt, develops a positive pregnancy test or gives other evidence of pregnancy, is incarcerated, initiates any excluded medication, or discontinues ECT before completion of the treatment series (e.g. because of adverse effects, lack of efficacy, or loss to follow-up). In addition, the principal investigator retains the right to withdraw participants from the study without their permission, in the event they are unwilling or unable to maintain adherence to the research protocol.

C. Procedures

1. Overview

All procedures performed by study personnel are researchrelated, but will be performed in addition to routine care (see Table 1). None of the study activities will be considered standard of care. There will be no cost to study subjects for their participation. Participants will be compensated for their time and travel. Study visits will be supervised by a boardcertified/board-eligible psychiatrist or psychiatry

resident and will be conducted either by a boardcertified/board-eligible

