any questions asked by the subject will be answered honestly and free of bias. A specific meeting time will be set up between a study team member and the participant where the entire informed consent document will be carefully explained in its entirety. The length of the meeting will be designed so there is the necessary amount of time for all questions to be answered.

To determine if an individual is eligible for study participation, a screening visit will be conducted. Initially, a HAM-D17 will be administered to determine if the patient exhibits depressive symptoms that are sufficiently severe for inclusion in the study. Next, the Mini International Neuropsychiatric Interview (MINI) will be administered to confirm a diagnosis of a current major depressive episode. Study subjects will receive a baseline basic metabolic panel (BMP) to assess for renal insufficiency, and vitals (these may have been obtained in the course of ongoing clinical care). The QIDS, Antidepressant Treatment Response Questionnaire (ATRQ), Clinical Global Impression (CGI), Beck Suicide Scale (BSS), and a MoCA will be administered. Each participant will be assessed for history of ECT therapy, current medications, and any other medical history.

Once entered into the study, depressed subjects will be randomized to receive either creatine or placebo using a random-digit method that is based on computer-generated numbers. Block randomization created by Investigational Drug Services (IDS) will be used to ensure equal treatment allocation within each block. 50% of the trial's clinical subjects will be randomized to placebo and the other 50% to active treatment. The study will be conducted as a double-blind trial, with neither participants nor research staff aware of participant assignment. Except in cases of medical emergency, the double-blind will not be "broken" until recruitment is closed and the final participant has completed 6 weeks of treatment and 4 weeks of follow-up. The blind will be broken following the culmination of the study or at the request of a medical professional dealing with a medical emergency in a case in which it would help a study participant.

2. Electroconvulsive Therapy

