³¹P-MRS; this will be administered in 4 divided doses of 5g each. Participants will then receive 5 g creatine daily throughout the course of ECT therapy (~3 weeks), with continuation for an additional 2 weeks after the completion of the acute series of ECT, again at 5g daily (thus, up to 5 weeks total supplementation with creating 5g per day, depending on the length of ECT) Placebo recipients will receive an inert, relatively tasteless powder matched to creatine (e.g., glucose). Creatine doses are based on doses that have previously been shown to be safe and efficacious [67-69].

3. Measures

We plan to use the following for determining participant baseline and data collection:

- Hamilton Depression Rating Scale (HAM-D17) (at baseline, the end of week 1, the end of week 2, the end of week 3, and two weeks after completion of the ECT series)
- Quick Inventory of Depressive Symptomatology (QIDS) (at baseline and prior to each ECT session)
- Antidepressant Treatment Response Questionnaire (ATRQ) (at baseline)
- Mini International Neuropsychiatric Interview (MINI) (at baseline)
- Clinical Global Impressions Scale (CGI) illness improvement subscale (CGI-I) (at baseline, week 1, week 2, week 3, and two weeks after completion of the ECT series)
- Beck Suicide Scale (BSS) at baseline, week 1, week 2, week 3, and two weeks after completion of the ECT series)
- Montreal Cognitive Assessment (MoCA) at baseline, week 1, week 2, week 3, and two weeks after completion of the ECT series)

4. Imaging

a. Magnetic Resonance Imaging (Siemens 3T MRI system)

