Aim 1: To evaluate the effect of creatine supplementation on response to ECT over the course of 6 weeks among persons with MDD.

As this is a pilot study, we have limited information regarding the potential magnitude of the effect of creatine supplementation on HAM-D scores in patients receiving ECT. Based on a prior recommendation that one assume a minimum detectable score of 7 for the HAM-D in randomized control trials, with a moderate effect size of 0.875 [72], we estimate that a sample size of 30 depressed subjects (15 active vs. 15 placebo) will have ~82% power to detect a significant difference between groups using a linear mixed model with first-order autoregressive covariance structure.

Aim 2: Aim 2: To evaluate the effect of 6 weeks of creatine supplementation on ³¹P-MRS neuroimaging data among persons with MDD.

Following 8 weeks of oral creatine, adult female methamphetamine users had significantly increased PCr levels [73]. The standardized effect size was 0.920. Also, a study involving openlabel creatine supplementation in depressed adolescents demonstrated significantly increased PCr levels following creatine administration [68]. The change of PCr levels was approximately 6.2% of the mean with 9.6% SD. Therefore, if we set the anticipated minimum detectable effect size (MDES) = 9% with SD = 10% for this project, a total sample size of 30 (15 active vs. 15 placebo) would have ~80% power to detect the anticipated effect using a repeated measures design.

VI. Administrative Procedures

A. Study Drug Administration

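### Participants who stop ECT early or are hospitalised for suicidality leave the study with no later rating provided for, so response, remission, time-to-event and MoCA comparisons can be biased, in a direction that cannot be predicted

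*Combined protocol and SAP*

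**What the plan says.** Section IV.B opens with "A participant will be withdrawn from the study" and lists the reasons. Two bear directly on outcome: "hospitalization for suicidal ideation or suicide attempt", and a participant who "discontinues ECT before completion of the treatment series (e.g. because of adverse effects, lack of efficacy, or loss to follow-up". Other listed reasons, such as pregnancy or incarceration, need not be related to outcome.

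Section IV.C.3 sets HAM-D17 at baseline and weekly, the last entries being "the end of week 3, and two weeks after completion of the ECT series". MoCA follows the same pattern: "Montreal Cognitive Assessment (MoCA) at baseline, week 1, week 2, week 3, and two weeks after completion of the ECT series". The Study Timeline in IV.C.1 adds week-4 ratings and uses the same post-ECT anchor. QIDS is taken "at baseline and prior to each ECT session", so it ends when ECT ends. No section describes an early-termination visit or any rating after withdrawal. Nothing says that ratings already made are discarded.

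Section V plans the Aim 1 comparison "using a linear mixed model with first-order autoregressive covariance structure", with 15 per arm and about 82% power. It names no analysis for response, remission or time to either, has no Aim 3 (MoCA) paragraph, and gives no analysis set, dropout allowance or censoring rule. Data Collection and Management gives only a database code for missing values.

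**The concern.** Stopping ECT for lack of efficacy is related to outcome by definition, and hospitalisation for suicidality is close to it. Stopping for adverse effects may include cognitive effects, which are the subject of Aim 3. These participants lose the remaining weekly ratings and the final one, because a person who stops early never reaches the point from which the final rating is counted.

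The exposure differs by endpoint. A likelihood-based mixed model for HAM-D scores uses everything recorded before withdrawal. The other Aim 1 hypotheses (response, remission, time to each) and the MoCA comparison have no stated method. If withdrawn participants are left out, or censored at withdrawal as though they were like those who stayed, the contrast between arms can be distorted. Ratings that were never taken cannot be recovered at analysis.

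**Working it through.** **Inputs.** From the documents: 15 per arm, standardised effect 0.875 and about 82% power (section V); 58% ECT response in treatment-resistant depression (section II.B). Assumed, because the documents give no values: 75% response on creatine, all withdrawal rates, two-sided alpha 0.05, the visit correlation, and the timing of responses.

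**1. The plan's power figure.** A plain two-sample t comparison at 0.875 with 15 per arm gives 63.8%. With four AR(1) post-baseline visits and a constant effect, the information per participant is (4 − 2ρ)/(1 + ρ). Choosing ρ = 0.692 makes this 1.546, the noncentrality 0.875 × √(15 × 1.546/2) = 2.98, and the power 82.0%. The stated figure is therefore attainable, but the plan's own inputs do not confirm it. I calibrate to it below.

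**2. Power loss.** A participant with only the first post-baseline score keeps 1/1.546 = 65% of the information.

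| Leave per arm | After week 1, scores used | After week 2, scores used | All data discarded |
|---|---|---|---|
| 1 of 15 | 81.1% | 81.4% | 79.1% |
| 2 of 15 | 80.1% | 80.8% | 75.8% |
| 3 of 15 | 79.2% | 80.1% | 72.1% |

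**3. Completer response, equal shares of non-responders withdrawn.** With true response p and share q of non-responders withdrawn, the completer rate is p/[p + (1 − p)(1 − q)]. The true difference is 75 − 58 = 17 points.

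| q | Placebo | Creatine | Difference | Share of arm withdrawn: (1 − p)q |
|---|---|---|---|---|
| 0.25 | 64.8% | 80.0% | 15.2 | 10.5% vs 6.3% |
| 0.50 | 73.4% | 85.7% | 12.3 | 21.0% vs 12.5% |
| 0.75 | 84.7% | 92.3% | 7.6 | 31.5% vs 18.8% |

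The last column matters: equal shares of non-responders are not equal withdrawal rates.

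**4. Completer response, equal withdrawal rates.** If a fraction d of each arm leaves, all non-responders, the completer rate is p/(1 − d) and the difference is 17/(1 − d):
- d = 10%: 64.4% vs 83.3%, difference 18.9 points.
- d = 20%: 72.5% vs 93.8%, difference 21.3 points.

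The sign of the bias is the reverse of step 3.

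**5. Time to response.** Spread responders evenly over four ratings and censor a fraction w of the arm, all non-responders, after the first. The Kaplan-Meier response at the last rating is 1 − (1 − p/4)(1 − p − w)/(1 − p/4 − w). With w = (1 − p)q and q = 0.25, 0.50, 0.75, the differences are 15.6, 13.1 and 8.5 points. With w = 10% or 20% in both arms they are 19.1 and 22.1 points. The reversal is the same.

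**6. False differences, true response 58% in both arms.**
- Equal shares, or equal rates with the same mix: 0.
- Unequal shares, 25% vs 50% of non-responders: 64.8% vs 73.4%, 8.6 points (8.1 by Kaplan-Meier).
- Equal 20% withdrawal but a different mix: one arm loses only non-responders, 0.58/0.80 = 72.5%; the other loses half responders and half non-responders, (0.58 − 0.10)/0.80 = 60.0%. The gap is 12.5 points.

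**7. Scale.** The standard error of a response difference at 15 per arm is √(0.58 × 0.42/15 + 0.75 × 0.25/15) = 17.0 points, or √(2 × 0.58 × 0.42/15) = 18.0 points at 58% in both arms. The largest completer shifts are (17 − 7.6)/17.0 = 0.55 and 12.5/18.0 = 0.69 standard errors.

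**The case against.** The case against acting is that the mixed model handles dropout, the trial is double-blind ("with neither participants nor research staff aware of participant assignment"), the illustrated shifts are below one standard error, and this is a 30-person pilot. The bias also depends on analyses the plan never states. Two features narrow the gap. Section IV.C.2 lets the treating psychiatrist set the number of treatments by clinical response, so a short series is not necessarily an incomplete one. It also takes QIDS from the clinical record, so a hospitalised participant who continues ECT may still have QIDS scores.

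Much of this stands. It limits the size of the point and clears the mean HAM-D analysis if stopping depends on recorded scores. It does not supply the missing HAM-D17 and MoCA ratings.

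A reader might infer from blinding that the bias is conservative, only diluting a true effect. The documents do not support that. Blinding makes similar stopping a reasonable starting point, but equal shares of non-responders shrink the difference and equal withdrawal rates enlarge it. Nor does a false difference require unequal rates; a different mix of responders and non-responders is enough, and adverse effects are a named reason that responders could also meet. Blinding does not guarantee an equal mix if creatine affects efficacy or tolerability.

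A reader might equally infer that the trial will produce a false benefit, or that withdrawn participants' data are thrown away. Neither is stated or derivable.

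**Conclusion.** The gap is real. Following section IV.B as written loses outcome-related ratings, and nothing in section V protects response, remission, time-to-event or MoCA results from that loss. The mean HAM-D comparison is much less exposed: close to unbiased if stopping depends on recorded scores, with power falling from about 82% to 79–81% if one to three per arm leave after week 1 and their early scores are used.

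Neither size nor direction can be derived for the other endpoints. The figures of 15, 12 or 8 points and of 19 or 21 points, against a true 17, rest on assumed rates, an assumed 75% response and withdrawal of non-responders only. The illustrated shifts are at most about half to two-thirds of a standard error, and no MoCA magnitude can be given. Confidence is high that the provision is missing, and low about how much it would matter in this sample. It should be fixed because the remedy is cheap and the data cannot be regained later.

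**What to change.** Leave the clinical reasons for stopping ECT or study drug as they are, and separate stopping treatment from stopping outcome collection.

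- **Ratings.** Continue HAM-D17 and MoCA at all remaining scheduled time points, counted from the start of ECT. Add a rating two weeks after the last ECT received if that is not already covered. Name in advance which rating is final. Exceptions: consent withdrawn, or participation not permitted (section VII.D notes the study is not approved for prisoners).
- **Analysis.** Include all randomised participants as assigned, with every recorded rating. A response or remission recorded before withdrawal keeps its date and counts as an event in the time-to-event analysis. State the censoring rule for the rest.
- **Final-visit response and remission.** Use the later rating where it exists. Apply non-responder imputation only to those with no later rating and no recorded response, with a sensitivity analysis.
- **Reporting.** Give withdrawals by arm and reason, and missing final MoCA scores by arm.
- **Reconcile** Aim 3's 8-week MoCA with the schedule, which has no such visit: up to four weeks of ECT plus two weeks of follow-up is six.

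The cost is protocol wording and a few ratings per withdrawn participant. Section VI.D pays $15 per follow-up visit; the five scheduled come to 5 × $15 = $75, already inside the $200 maximum (25 + 50 + 75 + 50). An added rating outside those visits would be a further $15. Some participants will decline, and those lost to follow-up cannot be recovered.
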